APPENDIX 10: Literature Cited	

1. EXECUTIVE SUMMARY

1.1 Title of Study

Self-administered cognitive behavior therapy for IBS: A multi-center study

1.2 Trial Acronym

IBSOS (Irritable Bowel Syndrome Outcome Study)

1.3 Study Purpose

This multi-site clinical trial is designed to assess the short- and long-term efficacy of cognitive behavior therapy (CBT) for irritable bowel syndrome using two treatment delivery systems (self-administered, therapist-administered). Secondary aims seek to specify the conditions under which CBT may (or may not) achieve its effects (moderator questions), why and how these effects are achieved (mediator questions) and to determine the economic cost and benefits of the therapies. Long-term project goals are to develop an effective self-administered behavioral treatment program that can enhance the quality of patient care, improve clinical outcomes, and decrease the economic and personal costs of one of the most prevalent and intractable GI disorders.

1.4 Objectives

- *Primary*: Evaluate the short-and long-term effects of a minimal-contact, homebased, patient-administered version of CBT compared to a standard, clinic-based, therapist-administered version of CBT and a psychological placebo (attention control) condition on improving global IBS symptoms.
- Secondary: To identify clinically useful patient characteristics associated with outcome as a way of gaining an understanding of subgroups of participants for whom CBT is most beneficial; to identify theory-based change mechanisms (active ingredients) that explain how and why CBT achieves therapeutic objectives; to evaluate the economic costs and benefits of CBT relative to control conditions.

1.5 Population

Male and female participants 18-70 (inclusive) years of age, suffering from IBS as defined by the Rome III criteria.

1.6 Treatment Arms

- Minimal Contact Cognitive Behavior Therapy (MC-CBT)
- Standard Cognitive Behavior Therapy (S-CBT)
- Attention Control Condition (ACC)

2. STUDY SCHEDULE AND TIMELINE

IBSOS is a prospective, randomized, multi-site clinical trial comparing three types of psychotherapy delivered in an individual format for severely affected adults with IBS. After a four-week baseline data collection period, participants will be randomly assigned to receive either four-session self-administered CBT, 10-session therapist-administered CBT or a control condition emphasizing support and education (allocation 1:1:1). The acute treatment phase will last 10 weeks. Participants will undergo follow-up examinations two weeks after treatment ends (week 12) and three, six, nine, and 12 months after the end of treatment.

IBSOS requires the expeditious enrollment of a sufficient number of participants to ensure the statistical power and generalization of study results. This trial plans to recruit 480 participants over an approximately four-year treatment delivery period. Assuming a relatively conservative pre randomization dropout rate of 25%, each site will need to phone telephone screen approximately 150 participants per year and enroll (consent) 75 in order to meet yearly recruitment quotas of 60 randomized participants at each site.

2.1 Duration of Study and Visit Schedule

After a one-year clinical trial planning phase, the study will begin recruitment of 480 Rome diagnosed adults. Recruitment is scheduled to occur over 48 months. The acute treatment phase will be administered over 10 weeks. Participants assigned to standard CBT will attend 10 weekly sessions. Participants assigned to either the limited contact or attention control treatments will attend four clinic visits scheduled over 10 weeks. Participants will undergo post-treatment evaluation two weeks after their assigned treatment ends (week 12) and at quarterly intervals (three, six, nine, 12 months) out to 12 months. Follow-up of all participants will continue until the last participant randomized has completed 12 months of follow-up.

See Appendix 1: IBSOS Protocol Overview

See Appendix 2: IBSOS Detailed Work Flow

3. STUDY OBJECTIVES

The major objectives of the IBSOS clinical trial are:

3.1 Primary Objective

Aim 1. To evaluate the efficacy of MC-CBT compared to S-CBT and attention control for IBS.

Hypothesis 1: Both MC-CBT and S-CBT are superior to attention-control on the primary endpoint of global improvement of IBS symptoms and secondary endpoints of satisfactory relief of IBS symptoms, quality of life, change in stool consistency, psychological distress, IBS symptom severity, participant satisfaction, and health care use.

Hypothesis 2: Equivalence testing will show that MC-CBT does not differ from S-CBT on primary (global IBS symptom improvement) or secondary endpoints.

3.2 Secondary Objectives

Aim 2. To identify clinically useful participant characteristics associated with outcome as a way of gaining an understanding of subgroups of participants for whom CBT is most beneficial.

Hypothesis 1: Variables such as treatment motivation at baseline and rapid treatment response will be positively associated with treatment outcome after the acute treatment phase of CBT and through follow-up periods.

Hypothesis 2: Interpersonal distress and extra-intestinal medical problems at baseline will be negatively associated with treatment outcome after the acute treatment phase of CBT and through follow up.

Aim 3. To identify theory-based change mechanisms (active ingredients) that explain how and why CBT achieves therapeutic objectives.

Hypothesis 1: Changes in the severity of IBS symptoms are partly mediated by changes in participants' beliefs regarding the causality (locus of control) and controllability (self efficacy) of IBS symptoms.

Hypothesis 2: Changes in the severity of IBS symptoms are partly mediated by nonspecific factors such as a strong therapeutic alliance and positive expectancy of improvement.

Aim 4. To describe the cost and cost effectiveness of MC-CBT, S-CBT and attention placebo for IBS.

Hypothesis 1: MC-CBT is associated with decreased direct and indirect cost compared to SCBT and associated with increased direct and indirect cost compared to attention control.

Hypothesis 2: MC-CBT will prove cost effective relative to either S-CBT or attention control.

Aim 5. To assess long-term durability of acute treatment effects of CBT at 3-, 6-, 9-, and 12 month follow-ups.

Hypothesis: Participants assigned to both CBT conditions will maintain treatment gains with respect to attention placebo through quarterly follow-up periods extending to 12 months after treatment completion.

3.3 Primary Efficacy Endpoints

The primary efficacy endpoint is as follows:

 Participant-rated global improvement of IBS symptoms. A participant is considered to be a treatment responder if s/he rates IBS symptoms for which s/he sought treatment as markedly to moderately improved using the Clinical Global Impressions Scale–IBS version.

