7. DATA ANALYSIS

7.1 Overview of Data Collection Schedule

In general, clinical interviews and questionnaires constitute the primary method of obtaining clinical data. The assessments described below were chosen according to the following principles:

- Use of standard, widely used or recommended assessment measures to maximize acceptance and comparability of findings with other studies
- Measures of multiple outcome criteria
- Psychometric properties, including established reliability and validity

The assessment will generate the following information:

- Data to be used for the screening of participants based on the inclusion and exclusion criteria
- Data to be used to evaluate the outcomes of treatment
- Outcome mediators and predictors

Data will be collected at three main stages of the trial: pre-treatment baseline, during active treatment, and at follow-up.

The main purpose of baseline assessment data is: (1) to confirm eligibility and (2) to obtain a reference level of functioning against which immediate and long-term treatment effects are to be judged. For this reason, most baseline measures will be re-administered at the end of treatment (two-week follow-up) and at quarterly follow-ups. Because a major goal of the IBSOS trial is to identify the active ingredient of CBT (i.e. mechanisms of change), a limited number of symptom measures *will be periodically assessed during the active treatment phase* along with a variety of "process" measures that tap psychosocial processes believed to account for treatment effects.

See Appendix 7: Data Collection Schedule

See Appendix 8: Description of Assessment Measures

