The **Patient-Reported Outcome Interview** (IBS Module PRO-IBS) ⁵⁷ is a semistructured interview whose 7 core items and 9 associated items correspond to Rome III criteria for IBS.

The IBS-PRO, in conjunction with physician decision making, can be used to support a current diagnosis of IBS in accordance with Rome III criteria. In addition to assessing the frequency and impact (distress, functional limitations) of key IBS symptoms (abdominal pain/discomfort, altered defecation, and associated symptoms such bloating, incomplete evacuation, nausea, urgency), the PRO-IBS taps the global impact of IBS symptoms on social, home/family, and occupational functioning, improvement in symptoms since baseline administration, overall response validity, and overall IBS severity. For each item, standardized questions and probes are provided to elicit description of symptom. These probes are designed to elicit the experience of IBS symptoms and their impact from the patient's perspective. The PRO-IBS is designed to be administered by clinicians and clinical researchers who have a working knowledge of IBS and Rome diagnostic criteria as well experience performing semi-structured diagnostic evaluations. The less clinical experience the potential interviewer has had, the more training required.

Outcome Assessment

Global Improvement / Relief

Consistent with Rome III recommendations ⁵⁸, the primary endpoint will be global improvement/relief of IBS symptoms. Global improvement of IBS symptoms will be based on a patient's response to the seven-point ordinal **Clinical Global Improvement Scale** (CGI-I)⁵⁹: "Compared to how you felt prior to entering the study, how would you rate the IBS symptoms for which you sought treatment during the past week?" (1 = very much improved, 7 = very much worsened).

We will adopt the practice ^{44, 47, 60} of defining responders as participants with a score of 1 (much improved) or 2 (very much improved) on the CGI-I. At post-treatment assessments, the study gastroenterologists (blind to treatment allocation) will complete a clinician-rated version of the CGI-I ⁴⁸ to estimate how much the participants' IBS symptoms improved or worsened relative to his or her baseline state.

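### The participant item behind the primary responder endpoint refers to the time before study entry, not the pre-treatment baseline, so change before randomization can count as treatment response

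*Protocol*

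**What the plan says.** Section 3.3 makes the primary endpoint a participant-rated responder status: "A participant is considered to be a treatment responder if s/he rates IBS symptoms for which s/he sought treatment as markedly to moderately improved". That sentence gives no date from which improvement is counted.

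Appendix 8 (Outcome Assessment, Global Improvement / Relief) gives the item: "Compared to how you felt prior to entering the study, how would you rate the IBS symptoms for which you sought treatment", rated for the past week on seven categories. The cut-off is stated as "defining responders as participants with a score of 1 (much improved) or 2 (very much improved) on the CGI-I". The same paragraph has the blinded study gastroenterologists complete a clinician version "to estimate how much the participants' IBS symptoms improved or worsened relative to his or her baseline state".

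On timing, Section 2 says "After a four-week baseline data collection period, participants will be randomly assigned". Sections 2 and 4.3 gloss enrolment as consent and plan 75 consented for 60 randomized per site per year. Appendix 4 describes the four weeks as a pre-treatment period before randomization, with medication held stable.

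Section 3.4 measures the change-type secondary endpoints (bowel function, pain and global severity, quality of life, psychological well-being, health care use, extraintestinal symptoms) from the pre-treatment baseline. Section 7.1 says one purpose of baseline assessment is "to obtain a reference level of functioning against which immediate and long-term treatment effects are to be judged".

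In Appendix 7, Global Impression of Change is absent from the baseline forms. It appears once during treatment (about week 5, as far as the table can be read), at all five follow-up visits and at premature discontinuation.

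**The concern.** A transition rating measures change from whatever moment its wording names. Here that moment most naturally lies before the run-in, so the rating spans at least four weeks in which nobody has been assigned or treated. A participant who improves in those weeks, through natural fluctuation after seeking care or through self-monitoring, can be scored a responder in any arm.

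The planned analysis cannot remove this. Sections 7.3 and 7.4 adjust each outcome for its own baseline score, which can absorb run-in change for scales measured at baseline. The global change item has no baseline value.

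Aim 1 (Section 3.1) rests both of its hypotheses on this endpoint: superiority of each CBT arm over attention control, and equivalence of MC-CBT and S-CBT. Where untreated change dilutes differences, it costs power for the first and favours the second. The participant and clinician versions of one scale may also count change over different intervals.

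**Working it through.** **The plan's own figure.** Section 7.4 gives about 65 and 85 per group for d = 0.50 at power 0.80 and 0.90. With two-sided 5% alpha (assumed; none is stated there), n = 2(z₁ + z₂)²/d²:

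- power 0.80: 2(1.960 + 0.842)²/0.25 = 62.8, so 63
- power 0.90: 2(1.960 + 1.282)²/0.25 = 84.1, so 85

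The figures reproduce, but they concern an adjusted mean difference. The Protocol gives no response rates, no power for the binary endpoint and no run-in improvement rate, so everything below uses assumed rates. Only the 160 per arm (Section 7.4) is the plan's.

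**Reference times side by side.**

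| Measure | Reference | Source |
|---|---|---|
| Participant item (primary) | before entering the study | Appendix 8 |
| Clinician version | baseline state, undated | Appendix 8 |
| Change-type secondary endpoints | pre-treatment baseline | Section 3.4 |

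With the present wording the rated change is run-in change plus post-randomization change. With a reference just before assignment it is post-randomization change alone.

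**Mechanism 1: a fixed share q reaches response during run-in and stays there.** The others respond at rate p. Present wording gives q + (1 − q)p. After re-anchoring, the early improvers report no change since assignment, so the rate is (1 − q)p. The difference is (1 − q)(p₂ − p₁) under both wordings. Power = Φ(difference/SE − 1.96), with SE = √{[r₁(1 − r₁) + r₂(1 − r₂)]/160} and r the observed rates. For q = 20%:

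| p₁ v p₂ | Present rates | Re-anchored rates | Difference, both | Power now | Power re-anchored |
|---|---|---|---|---|---|
| 40% v 60% | 52% v 68% | 32% v 48% | 16 points | 84.2% | 84.2% |
| 45% v 60% | 56% v 68% | 36% v 48% | 12 points | 60.6% | 59.1% |
| 30% v 50% | 44% v 60% | 24% v 40% | 16 points | 82.7% | 87.6% |

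Response rates are inflated by 20 points in each arm. The difference does not depend on the wording, and power moves only through the variance.

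**Mechanism 2: everyone shifts equally on a latent improvement scale with a fixed cut-off.** The rate becomes Φ(Φ⁻¹(p) + s). For s = +0.2 SD:

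- 20% v 35%: 15.0 to 16.6 points
- 30% v 45%: 15.0 to 15.7 points
- 50% v 65%: 15.0 to 14.2 points

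The difference grows at the lower rates and shrinks at the highest pair.

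**Mechanism 3: the same shift, with run-in change varying between people.** With 30% extra variance the rate becomes Φ[(Φ⁻¹(p) + 0.2)/√1.3]:

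- 20% v 35%: 15.0 to 14.9 points
- 30% v 45%: 15.0 to 13.8 points
- 50% v 65%: 15.0 to 12.7 points

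This is the most realistic of the three, and here the differences fall by 0.1 to 2.3 points. It treats run-in change as independent of later change. If severity has equal variance σ² at each time, the variance of change is 2σ²(1 − ρ). Re-anchoring then reduces noise only if severity at randomization correlates better with the outcome than severity at entry does. That is plausible, because it is closer in time, but not guaranteed.

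**Under no treatment difference**, randomization makes run-in change comparable across arms, so a zero difference stays zero under every mechanism.

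**The case against.** The strongest reply is that this is a wording point with no demonstrated cost. Much of it stands.

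- A reader might infer that every between-arm difference shrinks by (1 − q) and that re-anchoring recovers the lost power. It does not: early improvers who stay improved carry no treatment information under either wording, and a common shift can enlarge differences. For the same reason, re-anchoring would not cure an easier equivalence claim under mechanism 1.
- A reader might infer that Section 7.1 is contradicted. Its sentence concerns measures taken at baseline, most of which are repeated later. A transition item with no baseline administration is not strictly governed by it.
- A reader might infer that all secondary endpoints are change from baseline. Section 3.4 also lists adequate relief, satisfaction, rapid response and safety, which are not defined that way.
- The Protocol does not fix when a participant enters the study. Section 5.1 calls the randomization system an enrolment system, and Appendix 9 has consent obtained before enrolment. The reading as consent is the most natural one, not a proven one.
- A reader might infer that participant and clinician ratings cannot be compared. The clinician's baseline state is undated, and Appendix 4 allows the baseline to be delayed for infection before the gastroenterologist's evaluation, which suggests an evaluation near its start. The two references may nearly coincide.

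What the reply does not remove is that the primary item has an undefined reference that most naturally precedes an untreated four-week period, that nothing in Section 3.3 settles it, and that no baseline covariate can correct for it.

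**Conclusion.** The concern holds in a limited form. On the most natural reading, the participant item counts change from before the four-week untreated baseline, while the clinician version and the change-type secondary endpoints refer to baseline. Pre-randomization improvement can therefore enter the primary response rate in every arm, inflating it and adding variation unrelated to treatment.

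Type I error for superiority is unaffected. The effect on between-arm differences is uncertain in size and direction. Modest dilution is likeliest, on the assumption that run-in change varies between participants and is largely independent of later change. With no documented run-in improvement rate, no power figure should be attached to this point; those above only test the mechanisms.

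The change is worth making because it is cheap, makes the response rates mean what the trial needs, and aligns two versions of one scale.

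**What to change.** Reword the participant item so that it refers to the end of the pre-treatment baseline, for example to how the participant felt just before being assigned to treatment. Use this wording at every administration: the one during treatment, the five follow-up visits and premature discontinuation. Give the clinician version the same dated reference in place of the undated baseline state, and state the reference time in Section 3.3 so that the endpoint definition is complete.

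The cost is one phrase on two forms and one sentence in the Protocol. The small downside is that the participant wording departs slightly from that used in earlier work. The change should precede the first ratings, since a later switch would mix two versions of the primary endpoint.

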3.4 Secondary Efficacy Endpoints

Secondary efficacy endpoints include the following:

- Adequate relief of abdominal pain two weeks after the end of treatment phase and at quarterly intervals through 12 months
- Adequate relief of bowel problems two weeks after the end of treatment phase and at quarterly intervals through 12 months
- Change from pre-treatment baseline of lower GI function (i.e. stool frequency; stool consistency; severity of urgency, bloating and straining) to post-treatment, and at quarterly follow-ups
- Change from pre-treatment baseline in ratings of (a) severity of abdominal pain/discomfort and (b) global severity of IBS symptoms to post treatment and at quarterly follow-ups
- Change from pre-treatment baseline in indices of health related quality of life to post treatment, and at quarterly follow-ups
- The percent of participants who describe themselves as satisfied with assigned treatment at 2-week follow-up using the Client Satisfaction Scale.
- Change from pre-treatment baseline in psychological well-being (e.g. overall mental well-being and discrete emotional problems such as anxiety, depression, somatization) to post treatment, and at quarterly follow-ups

- Change from pre-treatment baseline in health care use to post-treatment, and at quarterly follow-ups
- Gains in estimated quality adjusted life years (QALYs) from pre- to post-treatment
- Change from pre-treatment baseline in extraintestinal symptoms to post-treatment, and at quarterly follow-ups
- The percent of participants responding positively to treatment as measured by the adequate relief of pain and adequate relief of bowel symptoms
- The percent of participants who report adequate relief, improved symptoms, and clinically significant reduction of IBS symptoms by week four (rapid response)
- Safety as measured by the occurrence of adverse events

The future status of global measures of relief/improvement as primary endpoints for IBS trials is unclear. The FDA, for example, contends that Rome recommended global endpoints (e.g. adequate relief) which IBSOS adopted are conceptually and methodologically problematic and have encouraged the development of a participant reported outcome (PRO) instrument that captures the key IBS symptoms and their day to day burden from the participants' perspective. Because the development of an IBS PRO is a time-consuming process whose completion would effectively suspend the development of novel biobehavioral treatments (CBT, drugs), the FDA has proposed interim endpoints for participants with IBS-D and IBS-C. These are described below. For IBS-C, a participant is regarded as a weekly responder on the basis of prospective improvement (from pre-treatment to post-treatment reduction during acute phase) in pain intensity *and* stool frequency.

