7.4. Formal Data Analysis

Aim 1

The primary focus of Aim 1 is to establish whether the effects of MC-CBT and S-CBT are comparable. We will pursue this from two perspectives: a traditional hypothesis testing framework and an equivalence testing framework. For the core outcome variables, we have assessments at baseline (BL), immediate post-test (FU W12) and at three-, six-, nine-, and 12-month follow-ups (FU3, FU6, FU9 and FU12) for each of three groups (MC-CBT, S-CBT and the active comparison control (attention control)). The traditional analysis for a given outcome variable is a two-way analysis of covariance

using the three groups as a between-participants factor, time as a within-participants factor (IM, FU3, FU6, FU9 and FU12) and the baseline score as a covariate. Single degree of freedom contrasts focus on the pair-wise comparisons of adjusted means within a given time period (e.g. comparing MC-CBT, S-CBT, and the attention control condition). Of interest is whether there are statistically significant pair-wise contrasts between the groups. We will pursue such contrasts using non-pooled error terms across time (because of the likely violation of sphericity), but with pooled error terms across groups within time (unless diagnostics suggest otherwise). We will use the program M Plus to estimate the single degree of freedom contrasts (by translating the analysis of covariance model into an SEM framework). M Plus has the capability to take into account cluster effects, should that be necessary, and it also offers robust algorithms.

In terms of statistical power, for a single degree of freedom contrast between two independent groups with a single covariate, the approximate sample size needed to achieve power of 0.80 for an adjusted mean difference of d = 0.50 (using Cohen's d) is approximately 65 per group. To achieve power of 0.90 requires a sample size of 85 per group. Our sample sizes easily meet these standards.

Aim 5

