DATA COLL	ECTION FOF	RMS	SCF	ĒD	ULE		00-00-00	
	STUDY IBSOS1 - B	00K 3						
NOTE: The columns are marked with an "X" to indicate			FOLLO	W-UP PE	RIODS			
data and evaluations required at each visit	Months	1	3	6	9	12	Premature	
	Weeks →	12	22	34	46	52	Discontinuation	_
FLIPS FORMS (continued)	Frontier Form #/ Reference							
ASI	asi	×	×	×	×	Х	×	_
ISN	vsi	×	×	×	×	×	×	
DIS	dis	×	×	×	×	×	×	
PSWQ-A	pswga	×	×	×	×	×	×	_
ER	er	×	×	×	×	×	×	
BDI-II	bdiii	×	×	×	×	×	×	
BSI-18	bsi18	×	×	×	×	×	×	_
STAI-SF	staisf	×	×	×	×	×	×	-
K-ESS	kess	×	×	×	×	×	×	
ISEL-12	isel 12	×	×	×	×	×	×	-
IIP-32	iip32	×	×	×	×	Х	×	
NIS	nis	×	×	×	×	×	×	-
WAI-SR-PATIENT	waisrpt	×					×	
WAI-SR-THERAPIST	waisrth	×					×	-
Adequate Relief	addrel	×	×	×	×	×	×	-
Global Impression of Change	gloc	×	×	×	×	×	×	
TSRQ (B)	tsrqb	×	×	×	×	×	×	
Client Satisfaction Questionnaire4	csq	х					×	
Site-Use Only forms (Not Entered into Database)								
Locator Form		×	×	×	×	×	×	

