The **Client Satisfaction Questionnaire-8** (CSQ-8) ⁸³ is an eight-item instrument of general satisfaction with treatment. It will only be administered at week 12. In addition, respondents will complete a single-item treatment satisfaction scale ("During the past week, how satisfied are you with the level of IBS relief your current treatment provides?"), with treatment responses ranging from 0 = very dissatisfied to 4 = very satisfied, that will be embedded in the end-of-week section of the daily diary.

Health Care Utilization/Cost

A critical component of the study is an economic evaluation (e.g. cost, costeffectiveness, and benefit-cost analyses) of the CBT treatment options. Some of the data needed for the economic evaluation will be collected in the **Economic Form-IBS**⁸⁴. This form includes a series of questions on health status and activity limitations, labor market activity, and health care insurance coverage. In addition, the form collects detailed information on health care utilization including the type and amount of new, or previously administered, treatments (including prophylactic), their focus, and associated costs (e.g. direct costs for diagnosing, treating, prescriptions, OTC agents, physician visits, alternative and complementary therapies) and patient costs of accessing these services (e.g. transportation, child care). Information from this form will be used to estimate the economic benefits and costs associated with the CBT treatment options. We will administer the Economic Form-IBS at major assessment periods (baseline, post-acute treatment phase, and quarterly follow-up visits).

Treatment Mediator Assessment

This set of measures is designed to help clarify the psychological processes that explain why CBT works or how it produces change (i.e. active ingredients) in IBS symptoms. These measures are completed at regularly scheduled times during the active treatment phase and at follow-up periods.

Control Beliefs

The 25-item **IBS Management Self Efficacy Scale** (IBS-SE) measures participants' confidence in their ability to control and manage IBS episodes using a seven-point Likert scale (1 = strongly disagree, 7 = strongly agree) ⁴¹. The **IBS-Specific Locus of**

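### Section 3.4 fixes participant satisfaction as an undefined percent satisfied although an eight-item questionnaire is collected; using the score would be a low-cost gain in precision on a secondary endpoint

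*Protocol*

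**What the plan says.** Section 3.4 of the protocol defines the satisfaction endpoint as "The percent of participants who describe themselves as satisfied with assigned treatment at 2-week follow-up using the Client Satisfaction Scale". It gives no item, score or threshold that makes a participant count as satisfied, and cites no source for the split.

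Appendix 8 (Treatment Satisfaction) names the instrument as the Client Satisfaction Questionnaire-8, which "is an eight-item instrument of general satisfaction with treatment. It will only be administered at week 12". The same paragraph adds a separate single satisfaction item, rated 0 to 4, in the end-of-week part of the daily diary. Appendix 7 lists the form as "Client Satisfaction Questionnaire4", and section 3.4 calls it a Scale, so three names are in use. The trailing digit in Appendix 7 may come from reading the PDF.

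Section 3.1, Hypothesis 1, claims superiority of both CBT arms over attention control on secondary endpoints that include "IBS symptom severity, participant satisfaction, and health care use". Hypothesis 2 reads "Equivalence testing will show that MC-CBT does not differ from S-CBT on primary (global IBS symptom improvement) or secondary endpoints", so it takes in satisfaction too.

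Section 7.4 (Aim 1) compares adjusted means. Its power statement says that the sample size for power 0.80 "for an adjusted mean difference of d = 0.50 (using Cohen's d) is approximately 65 per group", and it gives 85 per group for power 0.90.

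**The concern.** A graded instrument is collected, but the endpoint keeps only which side of a line each participant falls on, and the line is not drawn. Two things follow.

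First, the split costs precision. The cost grows as the share satisfied moves away from one half, so it is largest if most participants in every arm are satisfied.

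Secondly, an undefined cut leaves room to choose it after the data are seen. The protocol handles its other yes/no outcomes differently. The global improvement responder follows cited practice, adequate relief is itself a yes/no question, and the FDA interim responders have explicit thresholds. In the same section 3.4 list, symptom severity, quality of life and psychological well-being remain change scores.

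At stake are some power for the satisfaction part of Hypothesis 1 and some precision in the MC-CBT versus S-CBT comparison. The primary endpoint is not affected.

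**Working it through.** **Inputs from the protocol.** d = 0.50 (section 7.4, Aim 1); 160 per arm (section 7.4, Equivalence Testing; also 480 participants allocated 1:1:1, 480/3 = 160).

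**Assumptions.** Two-sided 5%, which section 7.4 does not state for its power figures. A normal latent satisfaction score shifted by 0.50 SD under CBT. A share p of controls satisfied, which the protocol does not give, varied here from 50% to 90%.

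**1. The plan's own figures.** n per group = 2(z₀.₉₇₅ + z_power)²/d².
- Power 0.80: 2(1.960 + 0.842)²/0.25 = 62.8, so 63 (64 with the t distribution). The plan says about 65.
- Power 0.90: 2(1.960 + 1.282)²/0.25 = 84.1, so 85 (86 with t). The plan says 85.

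Both reproduce, which supports the two-sided 5% assumption.

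**2. Mean score, 160 per arm.** Power = Φ(d√(n/2) − 1.960) = Φ(0.50 × √80 − 1.960) = Φ(2.51) = 99.4%.

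**3. Percent satisfied, same underlying effect.** The CBT share is q = Φ(Φ⁻¹(p) + 0.50). With p̄ = (p + q)/2, s₀ = √(2p̄(1 − p̄)/n) and s₁ = √([p(1 − p) + q(1 − q)]/n), power = Φ([q − p − 1.960 s₀]/s₁). The information lost at the cut is 1 − φ(z_p)²/[p(1 − p)], where z_p = Φ⁻¹(p).

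Example at p = 80%: q = 0.910, s₀ = 0.0394, s₁ = 0.0389, so power = Φ((0.110 − 0.077)/0.0389) = 80.2%. Information lost = 1 − 0.280²/0.16 = 51%.

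| Controls satisfied (assumed) | CBT satisfied | Power | Points below 99.4% | Information lost at the cut |
|---|---|---|---|---|
| 50% | 69% | 94.1% | 5.3 | 36% |
| 60% | 77% | 92.4% | 7.0 | 38% |
| 70% | 85% | 88.6% | 10.8 | 42% |
| 80% | 91% | 80.2% | 19.2 | 51% |
| 85% | 94% | 72.4% | 27.0 | 57% |
| 90% | 96% | 60.1% | 39.3 | 66% |

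At power 0.80, the split needs 102 per arm at p = 50% and 160 at p = 80%, against 63 for the mean score. By that measure the loss is 1 − 63/102 = 38% to 1 − 63/160 = 61%.

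**4. Attrition.** With 128 per arm (an assumed 20% loss: 160 × 0.80), the mean score has 97.9% power. Percent satisfied runs from 88.2% at p = 50% to 70.9% at p = 80%.

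**5. Ceiling.** A simulation of a bounded score (assumed range 8 to 32, SD 5, cut at 24) with latent control shares of 60% to 90% gave 97% to 99% power for a t or rank test on the score, and 92% down to 55% for the split. The range, SD and cut are not in the protocol, so this shows only that a ceiling need not remove the advantage of the score.

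**6. MC-CBT versus S-CBT.** With share p in both arms, the 95% half-width for the difference in percent is 196√(2p(1 − p)/160): 11.0 points at 50% and 8.8 at 80%. Section 7.4 illustrates equivalence thresholds only for IBS-SS (50) and IBS-QOL (14), so these widths have no margin to be set against.

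**The case against.** The strongest reply is that no shortfall is shown. If 50% to 80% of controls are satisfied and nobody is lost, power stays at 80% to 94%, at or above the 0.80 standard of section 7.4, on one of 13 listed secondary endpoints. That stands. A reader might infer from the lost information that the trial is underpowered for satisfaction. The documents do not support this: power falls below 0.80 only with more than about 80% of controls satisfied, or with attrition, and the protocol gives neither figure.

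The d = 0.50 is also not a satisfaction effect. It is a generic adjusted mean difference with one covariate, and the CSQ-8 has no baseline value. That stands too; the power figures are illustrations.

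A reader might infer that the equivalence conclusion for satisfaction fails. With no margin on either scale, only reduced precision can be shown. Nor is the CSQ-8 the only satisfaction measure, since the diary carries the 0 to 4 item. That item does not supply a cut for the section 3.4 endpoint.

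Finally, a percentage reads easily and matches the trial's responder-style outcomes. The primary endpoint also sits outside a comparison of means, so departure from that framework is no argument by itself. The statistical analysis plan is not shown and may analyse the score. These replies limit the harm. They do not supply the missing cut or remove the gain from using the score.

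**Conclusion.** The point holds as a recommendation of modest weight. Section 3.4 fixes satisfaction as a percentage with no cut, while an eight-item instrument is collected at week 12 for an endpoint of both hypotheses. Under the assumed latent-normal model, the split costs 5 to 19 points of power, and 36% to 51% of the information at the cut, if 50% to 80% of controls are satisfied. At 85% to 90% satisfied the costs are 27 to 39 points and 57% to 66%. The shares satisfied are assumptions, so these sizes are conditional and not properties of the plan. Analysing the score is an efficiency gain on a secondary endpoint; no stated power figure is wrong.

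**What to change.** In section 3.4, make the week-12 CSQ-8 total score the satisfaction endpoint, and state how the total is formed. Compare arms on the mean score with a linear model containing arm and site (the randomisation stratum; there is no baseline value), with a rank-based or ordinal analysis as a check for ceiling. Use the same mean difference and confidence interval for MC-CBT versus S-CBT. If equivalence on satisfaction is to be claimed formally, state a margin in advance. Keep percent satisfied as a descriptive summary, with its cut defined before the data are seen. Use one instrument name in section 3.4, Appendix 7 and Appendix 8.

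The cost is a short rewording and one simple model on data already being collected. The downside is that a mean score is less directly readable than a percentage, which is why the percentage stays as a summary.
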